Medications	
Mandatory Medications:
 
 ▪ ABX464 or its matching placebo administered once daily; ▪ MTX ≥ 10 mg/week, at previous dose regimen kept stable throughout the study; the maximal dose of methotrexate should not exceed a total of 20 mg/week ▪ Folic acid ≥ 5 mg/week post MTX dose, to minimize MTX toxicity. 
Potential Drug-Drug Interactions (DDIs) with methotrexate: ABX464 is mainly metabolized by CYP1A2 and glucuro-conjugated. Methotrexate undergoes hepatic and intracellular metabolism to polyglutamated forms. Multiple DDIs have been documented with methotrexate. In this study, potential methotrexate interactions on ABX464 will be sought using an on-going PK modelling approach. For documented DDIs with methotrexate, please refer to the Appendix 5.
 
Allowed Concomitant Medications:
 
 ▪ Corticosteroids at stable dose of prednisone and prednisone equivalent ≤10 mg/day during the study; ▪ Non-steroidal anti-inflammatory drugs (NSAIDs) at stable dose during the study; ▪ Antalgics including class III at stable dose during the study; ▪ Other non-rheumatologic medications. 
Prohibited Concomitant Medications:
 
 ▪ Any non-anti-TNFα biological or targeted DMARDs: IL-6 antagonists, JAK inhibitors, CTLA-4Fc Chimera, rituximab; ▪ Any immunosuppressive drugs; ▪ Vaccination with live components during the study and up to 8 Weeks after the last dosing; ▪ Drugs that could interact with ABX464 should be avoided especially the CYP1A2 substrates. The following CYP1A2 substrates with a narrow therapeutic margin are prohibited during the whole course of the study (rifampicin, clozapine, theophylline, ropinirole, warfarin, and methadone). In case of concomitant treatment with ondansetron, the maximal daily dose must be limited to 8 mg; ▪ Use of any investigational or non-registered product within 3 months preceding baseline.
Premature trial discontinuation	
Patient's premature trial discontinuation must occur for the following reasons:
 
 ▪ Investigator's decision; ▪ An Adverse Event or an intercurrent condition that preclude continuation of treatment;

Study n° ABX464-301
	
Clinical Phase IIa Type of Study Safety, Tolerability, Efficacy Study

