	
 ○ Specifically, an increase $\geq 3.0 \times$ ULN in liver transaminases (AST/SGOT and/or ALT/SGPT) or an increase $\geq 2.0 \times$ ULN in Alkaline phosphatase or in total bilirubin requires close observation with repeating liver enzymes and serum bilirubin tests two times weekly and clinical investigation to understand the etiology of this elevation. Frequency of retesting can decrease to once a month if abnormality stabilizes after this initial two weeks of follow-up and if the patient is asymptomatic. Discontinuation of the study treatment should occur if: 
 • ALT or AST $> 8 \times$ULN • ALT or AST $> 5 \times$ULN for more than 2 weeks • ALT or AST $> 3 \times$ULN and total bilirubin $> 2 \times$ULN or INR>1.5 • ALT or AST $> 3 \times$ULN with appearance of fatigue, nausea, vomiting, right upper quadrant pain or tenderness, fever, rash, and/or eosinophilia ($>5\%$). ▪ Worsening of the RA (according to physician evaluation); ▪ Major protocol violation; ▪ Withdrawal of consent; ▪ Administrative reasons from Sponsor.

Patient Follow-up
	
On Day 84 +/- 2 days, patients willing to carry on the study treatment will be able to take part in an open-label study (ABX464-302). In any other case, the subjects will exit the study (EOS) and will be treated according to the standard of care. The ABX464-302 follow-up study is a separate clinical study subject to health authorities and ethics committee approvals.

Data Safety Monitoring Board (DSMB)
	
A Data Safety Monitoring Board with expertise and experience in the management of Rheumatoid Arthritis will review the safety of the trial. The DSMB will meet after the first 6 patients (i.e. 50mg) are dosed for at least 2 Weeks to check the 50mg dose tolerability. Once the DSMB recommendation is granted, the next 6 patients will be randomized to receive either ABX464 50mg, ABX464 100mg or placebo. A second DSMB meeting will then be held when these 6 next patients are treated for at least 2 weeks, to check the 100mg dose tolerability and grant the recommendation to resume patient's randomization.
 
In addition, from the first DSMB onwards, meetings will be held every month during the study period.

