5. STUDY ASSESSMENTS AND PROCEDURES

5.1. Study Flow Chart

A detailed study flow chart (with all assessments) is displayed hereafter.

	Screening Period	Study Treatment Period						Follow-up Period
	D-30 to D-1	D0	D7	D14	D28	D56	D84	D105
		W0	W1	W2	W4	W8	W12	W15
Time Window (time between two visits ≤ 30 days)			± 2 days	± 2 days	± 2 days	± 2 days	± 2 days	± 2 days
	Screening	Baseline	V1	V2	V3	V4	V5	EOS
Obtained Informed Consent	X							
Check of IN/EX Criteria	X							
Medical History	X							
Height Measurement (cm)	X							
Body Weight (kg)	X	X	X	X	X	X	X	X
Physical Examination	X	X	X	X	X	X	X	X
Vital signs	X	X	X	X	X	X	X	X
Concomitant Medications	X	X	X	X	X	X	X	X
ECG (12 lead)	X	X					X	X*
Blood Pregnancy test (WOCBP)	X				X	X	X	X
Urine Pregnancy test (WOCBP)		X						
Randomization		X						
ABX464/placebo treatment dispensation		X			X	X		
Hematology + Biochemistry#	X#	X	X	X	X	X	X	X
Blood samples drug PK (pre-dose)				X		X		X**
Blood samples drug PK (1-, 2- & 3- hours post-dose)		X		X		X		
Blood samples for Cytokines (gel tube)		X	X	X	X	X	X	
Blood samples for Cytokines (Truculture® tube)		X				X		
Blood samples for flow cytometry cells count***		X				X		
Blood samples for CRP, ESR	X	X	X	X	X	X	X	
Blood samples for miR-124 (Paxgene® tube)		X				X		
Tender Joint Count (28)	X	X		X	X	X	X	
Swollen Joint Count (28)	X	X		X	X	X	X	
Patient Global Assessment of Disease (PtGA-VAS)	X	X		X	X	X	X	
Patient assessment of Joint Pain (Pain-VAS)		X		X	X	X	X	
Investigator Global Assessment of Disease (PrGA-VAS)		X		X	X	X	X	
Health Assessment Questionnaire – Disease Index (HAQ-DI)		X		X	X	X	X	
Functional Assessment of Chronic Illness Therapy (FACIT)-Fatigue		X		X	X	X	X	
Patient diary (dispensation/check)		X	X	X	X	X	X	
Adverse Events recording	X	X	X	X	X	X	X	X
Follow-up Headache Questionnaire in case of persistent headache (see section 5.3.2)			X (throughout the study, if needed)					
Dermatologist consultation in case of skin effect (see section 5.3.2)			X (throughout the study, if needed)					

#Tests of TB, HIV, HCV, HBV only at screening; *ECG at EOS visit in case of early termination only; **trough levels PK samples; ***Only in French Coordinating Investigator's Site; Two visits should not be conducted more than 30 days apart

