6.2. Premature trial discontinuation

A patient can be withdrawn at any time from the study for the following reasons:

Patient's premature trial discontinuation could occur for the following reasons:

- Investigator's decision;
- An Adverse Event or an intercurrent condition that preclude continuation of treatment;
 - Specifically, an increase ≥ 3.0 x ULN in liver transaminases (AST/SGOT and/or ALT/SGPT) or an increase ≥ 2.0 x ULN in Alkaline phosphatase or in total bilirubin requires close observation with repeating liver enzymes and serum bilirubin tests two times weekly and clinical investigation to understand the etiology of this elevation. Frequency of retesting can decrease to once a month if abnormality stabilizes after this initial two weeks of follow-up and if the patient is asymptomatic. Discontinuation of the study treatment should occur if:
 - ALT or AST > 8 xULN
 - ALT or AST > 5 xULN for more than 2 weeks
 - ALT or AST > 3 xULN and total bilirubin > 2 xULN or INR >1.5
 - ALT or AST > 3 xULN with appearance of fatigue, nausea, vomiting, right upper quadrant pain or tenderness, fever, rash, and/or eosinophilia ($>5\%$).
- Worsening of the RA (according to physician evaluation);
- Major protocol violation;
- Withdrawal of consent;
- Administrative reasons from Sponsor.

A patient who prematurely exits the study will not be replaced.

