8.1.1. Protocol deviations

Protocol deviations will be reviewed and classed as major or minor during the blind-review meeting. Major protocol deviations are defined as deviations liable to bias the evaluation of the main efficacy endpoint. The following deviations will be considered as major (non-exhaustive list):

- Noncompliance with the inclusion or exclusion criteria;
- Noncompliance with the study treatment;
- Intake of prohibited medication;
- Noncompliance with time window.

In case of major protocol deviation, the patient must not be randomized (if deviation occurs at baseline) or be discontinued from the study.

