6.4 PER PROTOCOL SET

The Per Protocol dataset (PP population) is defined as those patients of the FAS population without any major protocol deviation.

Major protocol deviations are defined as deviations liable to bias the evaluation of the main efficacy endpoint. The following deviations will be considered as major (non-exhaustive list):

- Noncompliance with the inclusion or exclusion criteria;
- Noncompliance with the study treatment;

- Intake of prohibited medication;
- Noncompliance with time window.

Limited programming checks e.g. prohibited medication (based on agreed codes), lab results, may be requested and reviewed on an ongoing basis. Other potential exclusions e.g. incorrect dosing of study medication may be discussed at the DRM. The final decision on inclusion in the PP Set will be agreed and documented before database lock.

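### Read literally, Protocol 8.1.1 calls for discontinuing a patient over any missed visit window, including misses that do not meet the plan's own definition of a major deviation

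*Protocol*

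**What the plan says.** Protocol 8.1.1 gives a definition, a list and a consequence.

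- Definition: "Major protocol deviations are defined as deviations liable to bias the evaluation of the main efficacy endpoint". The main efficacy endpoint is ACR20 at Week 12 (Protocol 2.4).
- List: four kinds of deviation that are to count as major, described as non-exhaustive. One is time-window noncompliance, with no visit, assessment or size of miss attached. SAP 6.4 repeats it: "Noncompliance with time window".
- Consequence: "In case of major protocol deviation, the patient must not be randomized (if deviation occurs at baseline) or be discontinued from the study".

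Two other places deal with the consequence. The synopsis says "premature trial discontinuation must occur for the following reasons" and includes "Major protocol violation" among the reasons. Protocol 6.2 has nearly the same list but says "premature trial discontinuation could occur for the following reasons".

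The flow chart (Protocol 5.1; SAP 16.1) has a time-window row giving ± 2 days at every visit from Week 1 to Week 15, and SAP 3.4 repeats these windows. The PP set is the Full Analysis Set without any major deviation (Protocol 8.1.2, SAP 6.4).

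On who decides and when, Protocol 8.1.1 has deviations classed as major or minor at the blind-review meeting. SAP 9.4 holds that meeting once the final data are considered clean. SAP 6.4 adds: "The final decision on inclusion in the PP Set will be agreed and documented before database lock". The SAP does not carry over the discontinuation sentence.

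**The concern.** The list is wider than the definition. A Week 1 visit one day outside its window falls within the list, but it is hard to see how it could bias an ACR20 response measured at Week 12. The same holds for a late Week 15 visit, which comes after that endpoint has been measured.

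The consequence is also out of proportion. Stopping treatment over a timing miss ends the patient's exposure and forfeits the Week 12 assessment, so the rule does more damage to the endpoint than the miss. With the synopsis and 8.1.1 saying must and 6.2 saying could, two sites could treat the same miss differently and both be following the protocol. With 20 patients per arm and no replacement of patients who exit early (Protocol 6.2), each patient stopped this way counts.

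**Working it through.** The rule has no figure of its own to reproduce. The sample-size statement that it could touch does reproduce: with 20 per arm, 65% versus 25% and two-sided 10%, the pooled-variance formula is z = (0.40·√20 − 1.645·√(2·0.45·0.55)) / √(0.65·0.35 + 0.25·0.75) = (1.789 − 1.157)/0.644 = 0.98. That gives 83.7% power against the stated 84%. The fault is in the wording, not in that calculation.

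**Which misses meet the definition of major?**

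- Week 1: window Days 5–9, so Day 10 is out. The visit has no joint counts, VAS or HAQ-DI and dispenses no drug. CRP and ESR are taken (flow chart; Protocol 5.3.7). Its timing has little bearing on Week 12 ACR20.
- Week 15: window Days 103–107, so Day 108 is out. ACR20 has already been measured.
- Week 4 and Week 8: these can matter. They dispense drug (Protocol 5.7) and supply values for last-observation-carried-forward (LOCF) imputation in Efficacy Set 2. But dosing has its own criterion: SAP 5.1 sets noncompliance at below 80% or above 120%. Doses run from Day 0 to Day 83, which is 84. A 30-capsule bottle covers Days 0–29, so a Week 4 visit on Day 31 misses Day 30 only: 83/84 = 98.8%. The compliance rule accepts this; the time-window item does not.
- Week 12: a visit outside Days 82–86 moves the endpoint assessment itself. This one fits the definition.

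**What happens to a patient stopped at a Day 10 visit?**

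- If the last dose is on Day 10, 11 doses are taken and 84 − 11 = 73 are forgone.
- The end-of-study visit (Protocol 5.2.5) lists no joint counts, VAS or HAQ-DI, so ACR20 cannot be derived from it.
- Efficacy Set 1 needs Week 12 data (SAP 6.3.1): the patient is absent.
- Efficacy Set 2 carries forward from Week 4 (SAP 6.3.2): there is no Week 4 value and no derivable ACR20, so the patient is a failure. SAP 3.5 also still counts early terminators as failures.
- One patient is 1/20 = 5 percentage points of an arm.

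**How far could the PP set shrink?** This is illustration only. Assume that each visit is missed independently with probability q and that the blind review spares nobody. Over the five treatment-period visits the share excluded is 1 − (1 − q)^5, and the number left per arm is 20(1 − q)^5. If only Week 12 counted, 20(1 − q) would remain.

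| Assumed q | Excluded, any of 5 visits | Left of 20, any visit | Left of 20, Week 12 only |
|---|---|---|---|
| 2% | 9.6% | 18.1 | 19.6 |
| 5% | 22.6% | 15.5 | 19.0 |
| 10% | 41.0% | 11.8 | 18.0 |

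**The case against.** The strongest reply is that the plan does not work the way the literal text suggests. Classing belongs to the blind review, which has the definition in hand and so a documented ground for calling a Week 1 miss minor. That review comes when the data are clean, too late to discontinue anyone. The mandatory sentence sits in the statistics section, while the withdrawal section in the protocol body is permissive. The synopsis names major violations without linking them to visit timing. The SAP drops the sentence, flags out-of-window visits in its listings and carries on (SAP 10.1). For Week 12 and Week 15 misses, discontinuation would not change treatment, because the last dose is on Day 83.

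The stakes are also limited. The primary endpoint, treatment-emergent adverse events, is analysed on the Safety Set. ACR20 is a secondary endpoint interpreted descriptively, and the PP set feeds one supportive table, 14.2.1.3. Restricting PP timing to Week 12 is partly a choice; a stricter supportive set can be defended.

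Most of this stands, and it makes the point minor. It does not remove the point. If classing comes too late to act on, the mandatory sentence is either inoperable or left to sites to apply unaided. If the review spares a Week 1 miss, it departs from a list that says such deviations are to count as major. Either way the text needs correcting.

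**Conclusion.** The point holds as a wording fault of minor severity. The time-window item is unqualified, it reaches misses outside the plan's own definition of major, and the protocol gives conflicting instructions on whether such patients must be stopped. Where a site follows the mandatory wording, a patient stopped at Week 1 loses Week 12 ACR20 and most of the planned exposure.

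Three stronger readings are not supported:

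- A reader might infer that any window miss automatically costs the PP place. It does not: classing and set membership are settled at review before lock, against the definition.
- A reader might infer that a patient stopped at Week 1 has no post-baseline efficacy data. CRP and ESR are scheduled at Week 1; what is missing is a derivable ACR20 and a Week 4 value to carry forward.
- A reader might turn the illustration into an expected loss of patients or power. The documents give no miss rate and no sign that sites discontinue for timing, so the size is unknown. The table rests on assumed rates, independence across visits and a review that spares nobody.

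**What to change.** In the synopsis (premature trial discontinuation), Protocol 6.2 and Protocol 8.1.1, state that a visit-window miss alone does not lead to discontinuation, and that such patients stay on treatment and are assessed at Week 12 unless another stopping reason applies. Use the same verb, must or could, in all three places.

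In Protocol 8.1.1 and SAP 6.4, apply the time-window item only to misses that meet the definition of major: at minimum, a Week 12 ACR20 assessment outside Day 84 ± 2. Handle dosing gaps from late Week 4 or Week 8 visits under the existing treatment-noncompliance criterion.

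The cost is wording only. The downside is that the supportive PP set tolerates some early-visit timing misses, and dosing gaps stay in unless compliance falls below 80%. Since 0.80 × 84 = 67.2, a patient with 68 of 84 doses (81.0%, 16 missed) would remain, as the present compliance rule already allows.

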8.1.2. Definition of study analysis sets

The following datasets will be defined and used for the analyses:

- The **Safety dataset (SAF population)** is defined as those patients included in the study, who have received at least one dose of the study treatment.
- The **Full Analysis dataset (FAS population)** is defined as those patients included in the study, who have received at least one dose of the study treatment, and who have at least one baseline data.
- The **Intent-to-Treat (ITT population)** is defined as those patients randomized, regardless of whether the patient received a dose of study treatment or completed the study.
- The **Per Protocol dataset (PP population)** is defined as those patients of the FAS population without any major protocol deviation.

8.1.3. Patients/Patients disposition

The number and the percentages of patients enrolled and included in each of the populations will be tabulated. The reason for patient exclusions from each of the populations will also be listed. In addition, the number of discontinued patients with their reason for discontinuation will be tabulated.

8.1.4. Demographic and other baseline characteristics

Demographics and other baseline characteristics will be summarized by treatment arm. This analysis will be conducted on the FAS population.

8.1.5. Treatment compliance

Number of doses will be presented on the FAS population.

8.2. Efficacy Analysis

Analysis of efficacy data will be carried out in the Full Analysis Set in which subjects who prematurely terminate the study will be considered failures.

The primary efficacy endpoint of the study, the ACR20 response rate, will be compared in subjects who received a given dose of ABX464 or placebo by likelihood ratio chi-square test on a 10% two-sided level.

The result of the test will be interpreted in a descriptive manner therefore no adjustment for multiple comparison is applied.

In addition, descriptive statistics will be presented by treatment arm for all secondary efficacy variables for each measurement timepoints separately for the two study groups.

These statistics include:

- Continuous variables: mean, standard deviation, minimum and maximum, stratified 95% confidence intervals, median and quartiles will be presented.
- Categorical variables: counts, rates and stratified 95% confidence intervals for the rates will be calculated.

In addition to descriptive statistics, mixed model analysis of covariance will be conducted for the following measurements:

- The change from baseline in DAS28-CRP and DAS28-ESR
- The change from baseline in the individual components of the ACR20 response (CRP, TJC(28), SJC(28), Pain-VAS, PtGA, PrGA, HAQ-DI) and in ESR
- The change from baseline in SDAI and CDAI scores
- The change from baseline in miR-124 in total blood at Week 8

In this model, treatments and stratum will be fixed effects, subjects will be random effect, and baseline values of the respective measurements will be covariates. Other explanatory variables will also be allowed to be included in the model. In order to normalize eventual skewed distributions transformation of the data will also be considered. Study groups will be compared within this model framework. All p-values will be interpreted in a descriptive manner.

8.3. Pharmacokinetics

Population PK data analysis will be performed via three steps:

- Data preparation and exploratory: The analysis dataset will be created and formatted according to MONOLIX or NONMEM requirement using SAS®. An exploratory analysis by visual inspection of PK profiles/dose normalized PK profiles in natural and semi-log scale will be performed in order to anticipate the type of PK model (number of compartments, linear or saturable elimination, etc)
- Population PK model development: A PopPK model consists of four basic components:
 - The structural PK model, which defines the PK parameters and describes the plasma concentration-time profiles of ABX464 and its metabolite.
 - The inter-individual variability model component, which describes the inter-individual variability of PK parameters in the population
 - The residual error model component, which describes the underlying distribution of the error in the measured concentrations.
 - The covariate model component, which describes the influence of covariates such as demographic data on PK parameters.

The search for the final model will follow the following strategy:

- Selection of the simplest structural model, which predicts the plasma concentration as a function of time and dose, based on smallest objective function and by the pattern in the residual plots. The best estimation method, the most appropriate inter-individual variability (IIV) models, and the residual error model, are identified. The resulting model is called BASE model.
- Test of influence of selected covariates.

- Refinement of inter-individual variability model and residual error models
- Model validation: Goodness of fit plots will be assessed for each important step of model building. For the final model, a visual predictive check (an evaluation graph based on simulation) will be provided.

Data will be prepared using SAS version 9.2. Population analysis will be performed using MONOLIX version 2018 R1 or NONMEM version 7.2. Graphs will be provided using SAS.

8.4. Safety Analyses

Adverse events will be coded using the standard dictionary (MedDRA) down to the lower level term (LLT).

An overall summary table will be presented (Any adverse event, any treatment emergent adverse event (TEAE), any serious adverse event (SAE), death, any grade 3 or higher adverse events from baseline to the end of Study. This analysis will be conducted on SAF population.

Two periods will be defined for TEAE:

- Any adverse event which occurs or worsens from first dosing to Day 84;
- Any adverse event which occurs after Day 84.

Adverse events will be described by primary system organ class and preferred term. Numbers and percentage of patients, and number of occurrences of adverse event will be presented for:

- TEAE;
- Serious TEAE;
- TEAE leading to drug discontinuation;
- TEAE of grade 3 or 4;
- TEAE for which relationship with the study drug is recorded as possible or probable.

Analysis of safety will be performed on the safety data set consisting all subjects who received at least one dose of ABX464 in the study.

Primary safety endpoint, the rate of all treatment emergent adverse experiences, will be compared in subjects who received a given dose of ABX464 or placebo by likelihood ratio chi-square test on a 10% two-sided significance level.

Further assessment of safety will be based on the frequency of adverse events (with and without regard to causality) graded according to the CTC-AE Classification and also, the review of individual values for clinical laboratory data, vital signs and ECG focusing on the detection of abnormal values and PCSAs [potentially clinically significant abnormalities (PCSAs) determined upon investigator considerations].

Adverse events will be tabulated (counts and percentages) by group. All adverse events will be listed, and the data will be tabulated by body system/organ class. Adverse event tabulations will include all treatment emergent adverse events, which will be further classified by severity, and relationship to treatment and dose level.

Clinical laboratory parameters, vital signs, ECG will be summarized by using descriptive statistics (n, mean, SD, SEM, median, minimum and maximum). Number of patients with at least one abnormal value will be tabulated (counts and percentages) for each parameter in summary shift tables, by group and dose.

